11.0. MRI PROCEDURES

11.1. Image Acquisition: We will image subjects on a 3T Philips Achieva system using a protocol that acquires: A) data to allow automated tissue identification; B) diffusion weighted data; and C) BOLD data at rest and during the emotional dot-probe task. The protocol will acquire T1-weighted (6min), fluid-attenuated inversion recovery (FLAIR; 9min), and diffusion-weighted images (9min). We will assess intrinsic FC (7.5 min, 7700 total frames) while participants focus on a fixated cross. Subjects will then complete the emotional dot-probe task (30 min; Sect. C.9.f). These sequences tally approximately 60 minutes; we budget for a 90-min MRI to allow for the longer time needed to position older adults and to allow a brief break between sequences if needed.

11.2 Functional MRI Task: The emotional pictures dot-probe task is a computerized spatially oriented attention task. The dot probe task contains images taken from the International Affective Picture System (IAPS)-including neutral, positive, and negatively valenced images- and was developed to measure attentional bias toward emotional information. In this task the subject is presented with pairs of pictures presented on the left and right of the screen. Following a picture pair presentation an asterisk appears on either the right or left of the screen. The subject is instructed to indicate the side of the screen on which the asterisk appears via button press, as quickly as possible. The time between when the probe appears and when the subject presses the corresponding key to its location is recorded in milliseconds and used for the calculation of facilitation indices. The primary score from the task is an attentional facilitation index that is calculated separately for the slides of different emotional valence. For the negative facilitation index, it is calculated using the following formula: $\text{Facilitation} = 1/2 \times [(\text{Neutral Only/Probe Up} - \text{Negative Up/Probe Up}) + (\text{Neutral Only/Probe Down} - \text{Negative Down/Probe Down})]$. Thus, this index is calculated by subtracting the participant's average response time to probes replacing negative stimuli from their average response time to probes replacing neutral stimuli in the various neutral-neutral picture pairings. This formula controls for potential location effects (participant's tendency to attend to either the right or left location of the screen) by summing latencies for left and right picture locations and taking their average. The facilitation index for positive emotion slides is calculated in the same way. If the spatial location of the probe corresponds to the same spatial location where the participant's attention is allocated then their response to the probes' location will be faster.

11.3. Image Processing: WML Segmentation: WML identification and measurement will be done using the Lesion Segmentation Toolbox (126), implemented through the VBM8 toolbox in SPM8. In native space, each voxel on the T1 image is assigned as gray matter, white matter, or CSF. After bias-correction the FLAIR is coregistered to the T1 image. The toolbox initially creates a conservative binary WML map based on outlier values across the T1 and FLAIR images. Next, a lesion-growth algorithm using Markov Random Fields modeling extends this conservative map to define the extent of the lesions. This lesion map can then be normalized into study-specific space and used to calculate total cerebral WML volume. This process takes approximately 4 hours from the time the images are acquired from the scanner.

11.4 Repeat MRI (SUBSTUDY)

As an optional procedure, we will ask randomized depressed participants to have a repeat MRI after completing Study Phase 1 (the 8-week blinded, placebo-controlled escitalopram phase). MRI procedures will be the same as in the baseline assessment. We will ask participants about participating during enrollment however they may change their mind at any point during study participation. This adds no additional risks to the project.

While the purpose of the overall study is to examine how imaging may serve as a predictor of antidepressant response, the overall Aim of the substudy is to examine how neural network connectivity changes during the course of the 8-week trial. We hypothesize we will observe differences between individuals who do and do not remit during Phase 1, wherein individuals who remit will exhibit post-treatment network connectivity similar to nondepressed elders. We will also examine whether there are differences in the interval change between individuals who remit on active drug and those who remit on placebo.

Data on never-depressed elders will be drawn from a separate study (IRB 130360, Frontal Hypoperfusion Effects on Antidepressant Outcomes in Late-Life Depression, PI: [name]). We anticipate that results from this substudy will inform the application for this project's competitive renewal.

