- 11) ECT in last 6 months
- 12) A failed therapeutic trial of escitalopram in the current depressive episode (defined as at least 6 weeks of treatment at a daily dose of 10mg or higher)
- 13) Known allergy or hypersensitivity to escitalopram or bupropion
- 14) Current or planned psychotherapy

We will additionally enroll up to 60 older adults with no history of psychiatric or neurological illness in order to have 40 subjects with MRI data. Data gathered from this cohort will assist us as we interpret data from the depressed cohort. Entry criteria will be similar to those of the depressed cohort, but adjusted to reflect we want to enroll individuals without any history of depression or other psychiatric illness.

Nondepressed Cohort:**Inclusion Criteria:**

- 1) Age 60 years or older.
- 2) Mini-Mental State Exam \geq 24.
- 3) Ability to read and write English.
- 4) MADRS score \leq 8

Exclusion Criteria:**Diagnostic Issues:**

- 1) Current or past diagnoses of any Axis I psychiatric disorders
- 2) Any use of illicit substances (such as marijuana or cocaine) or abuse of prescription medications (such as benzodiazepines or opiates) within the last three months.
- 3) Presence of acute suicidality
- 4) Current or past psychosis

Medical Issues:

- 5) Known primary neurological disorder, including dementia, brain tumors, epilepsy, Parkinson's disease, or demyelinating diseases
- 6) Chronic untreated medical disorders (including but not limited to hypertension, hyperlipidemia, fibromyalgia, hypothyroidism, or any medical disorder) where treatment is warranted
- 7) Any physical or intellectual disability affecting completion of assessments
- 8) MRI contraindications

Antidepressant Treatment Issues:

- 9) Any history of antidepressant treatment, including antidepressant medications, psychotherapy, or brain stimulation such as ECT. Brief couples / marital counseling, where the focus of treatment was not a psychiatric illness is allowable.

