7.0. STUDY OVERVIEW

After consent, subjects will be evaluated for eligibility. After standardized clinical and cognitive assessments and MRI, subjects will begin 8-weeks of double-blinded study drug, either escitalopram or placebo. Those who do not remit, defined as a MADRS ≤ 7 at the last assessment, will enter an 8-week open-label trial of bupropion XL. Subjects will be evaluated every two weeks via monthly clinic visits and telephone visits at

intervening two weeks.

Nondepressed participants will only complete the screening and baseline assessments. They will not receive study medication or follow-up assessments.

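### The repeat-MRI substudy names an external never-depressed comparator of unstated comparability and not the trial's own nondepressed cohort, so study and diagnosis cannot be separated in the one contrast that needs controls

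*Combined protocol and SAP*

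**What the plan says.** Section 11.4 describes an optional second MRI after Phase 1 for randomized depressed participants, using the baseline imaging procedures. Its stated purpose is within-person: "the overall Aim of the substudy is to examine how neural network connectivity changes during the course of the 8-week trial". Three comparisons follow.

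- Remitters against non-remitters: "We hypothesize we will observe differences between individuals who do and do not remit during Phase 1".
- Remitters against a normal reference: "individuals who remit will exhibit post-treatment network connectivity similar to nondepressed elders".
- Remitters by arm: "differences in the interval change between individuals who remit on active drug and those who remit on placebo".

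For the second, "Data on never-depressed elders will be drawn from a separate study". That study is identified by its IRB number and title only. The section states no reason for the choice, no acquisition match, no eligibility criteria, no harmonisation step and no study term.

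The trial also has its own nondepressed cohort. Section 4.0 plans to "enroll up to 60 older adults with no history of psychiatric or neurological illness in order to have 40 subjects with MRI data" and excludes anyone with a current or past Axis I diagnosis, so by its criteria the cohort is never-depressed. Section 2.0 gives the number as 30. Section 7.0 limits what is collected: "Nondepressed participants will only complete the screening and baseline assessments". Section 11.1 sets one acquisition protocol, including resting BOLD on a 3T Philips Achieva. Section 15.0 brings the nondepressed data into the Aim 1 analyses with a group variable.

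**The concern.** A claim that connectivity has normalised depends on the reference group. If every remitter comes from this trial and every control from another, a difference in acquisition, processing or selection between the studies goes straight into the remitter-versus-control contrast. No model fitted to those data can take it out, because study and group are the same variable.

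The hypothesis is one of similarity, so an offset can mislead in two ways. It can make normalised remitters look abnormal, or it can cancel a real residual abnormality and make them look normal.

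The plan would also use two normal references: the in-trial cohort against depressed participants at baseline (Section 15.0) and the external cohort after treatment (Section 11.4). A statement that remitters moved towards normal is easier to defend if normal is the same group at both times. Because the in-trial scans are already planned, the exposure looks largely avoidable.

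**Working it through.** **No stated figure to reproduce.** Section 11.4 gives no sample size, effect size or test for the substudy, and Section 15.0 does not mention it.

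**Which contrasts are exposed**

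| Substudy comparison | Needs nondepressed controls? |
|---|---|
| Change over 8 weeks | No |
| Remitters vs non-remitters | No |
| Drug vs placebo remitters, interval change | No |
| Remitters' post-treatment connectivity vs nondepressed | Yes |

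One of the four is exposed.

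**Why the exposure cannot be modelled away.** With external controls alone there are two cells: remitters in this trial and controls in the other study. The observed difference is the true group difference plus the offset, and the two parts cannot be told apart. Adding in-trial controls gives three cells for three parameters (intercept, group, study), so group and study can both be estimated.

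**Illustration of size.** Inputs, all assumptions unless a source is given:

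- Remitters rescanned: 15, 20, 40 or 83. The top value is 130 × (1 − 0.36) = 83.2, using the evaluable sample and base non-remittance rate in Section 15.1 and supposing that every remitter accepts a second scan.
- Controls: 30 (Section 2.0) or 40 (Section 4.0). These are in-trial figures used as stand-ins, since the external number is not given.
- Offset δ: 0.2, 0.3 or 0.5 SD.
- Test: two-sided 5% two-sample z test with SD = 1.

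SE = √(1/n₁ + 1/n₂)

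Rejection rate = Φ(−1.96 − δ/SE) + 1 − Φ(1.96 − δ/SE)

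Example with 20 remitters and 40 controls: SE = √(0.05 + 0.025) = 0.274. At δ = 0.2, δ/SE = 0.73 and the rejection rate is 11.3%.

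Chance of declaring a difference when there is none:

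| Remitters / controls | δ = 0 | 0.2 SD | 0.3 SD | 0.5 SD |
|---|---|---|---|---|
| 15 / 30 | 5% | 9.7% | 15.8% | 35.3% |
| 20 / 40 | 5% | 11.3% | 19.5% | 44.7% |
| 40 / 40 | 5% | 14.5% | 26.9% | 60.9% |
| 83 / 40 | 5% | 18.0% | 34.4% | 73.8% |

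The first and last rows are the extremes of the grid.

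Masking uses the same formula with the true difference less the offset. For a true difference of 0.5 SD with 20 remitters and 40 controls, power falls from 44.7% with no offset to 19.5% at 0.2 SD and 11.3% at 0.3 SD.

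**The case against.** The strongest reply is that nothing in the documents shows the other study was imaged differently. Section 11.4 gives no scanner, sequence or site for it, so the acquisition may be identical. This stands. A reader might infer that the plan builds in an imaging difference, but the documents support only that equivalence is not stated.

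A reader might also take this to be the substudy's key comparison. It is not. The stated aim is change over eight weeks, and the remitter/non-remitter and drug/placebo contrasts lie wholly within the trial. The substudy is optional and meant to inform a renewal application.

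Nor do the documents say that the in-trial cohort is excluded from the substudy. Section 4.0 gives it a general role in interpreting the depressed cohort's data. What can be said is that 11.4 names a different source and does not name this one.

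Finally, in-trial controls would not guarantee a 5% error rate. They have one baseline scan, while remitters would be compared on a second scan after eight weeks of study drug. Their entry criteria also differ: Section 4.0 excludes nondepressed participants with chronic untreated medical disorders, and has no matching exclusion for the depressed cohort. In-trial controls remove the between-study risk but not scan-order, time or selection effects.

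These points narrow the concern without removing it. The plan names a comparator of unknown comparability while one scanned under the trial's own protocol is already being collected.

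**Conclusion.** The point holds as a minor one. In the comparison of remitters' post-treatment connectivity with nondepressed elders, and only there, study is fully aliased with diagnostic group under the comparator that 11.4 names. If an offset is present, the false-difference rate would be about 10-18% at 0.2 SD and 35-74% at 0.5 SD, instead of 5%, over the assumed range of 15 to 83 remitters and 30 to 40 controls. A real difference could equally be masked. If the two studies match, the rate does not change. The number rescanned, the external sample size and the offset are all absent from the documents, so these figures show sensitivity and do not estimate actual bias. No main trial aim is affected.

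**What to change.** In Section 11.4, name the trial's own nondepressed cohort, at its baseline scan, as the primary comparator for remitters' post-treatment connectivity. Use the external controls only in a sensitivity analysis that pools both control groups and includes a study term. State the external study's scanner, sequences and entry criteria there. Without covariates, that model's remitter-versus-control estimate still rests on the in-trial controls. What it adds is a direct estimate of the offset between the two control groups.

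Reconcile the cohort size: 30 in Section 2.0, and 40 with MRI from up to 60 enrolled in Section 4.0.

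The cost is a change of wording, with no new scan. There are two downsides. The primary comparator may be smaller than a pooled one. Its single baseline scan also leaves scan-order and time effects uncontrolled, which 11.4 should state as a limitation.

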12.0. POTENTIAL RISKS

1. **Interview, emergencies, and possible suicidal ideation.** Subjects may experience discomfort during the clinical interview and evaluations when discussing symptoms, life events, and social support. The Project Coordinator will be experienced and skilled in interviewing depressed subjects. Should the subject wish to stop or take a break, the coordinator will allow it. A study doctor will be available as a backup. In addition, should the subject express suicidal ideation at any time during the interview, a study doctor will be contacted immediately to assess the subject and to determine the appropriate course of action. Thoughts of suicide will be taken very seriously. Options for addressing this may include contacting the individual's mental health caregiver, referring for urgent evaluation and treatment, or emergent evaluation and hospitalization. Similar practices will be used for other emergencies, including but not limited to psychosis, homicidal or violent thoughts, or an acute change in a subject's physical status.
2. **Unblinding:** It is possible that it may be crucial to definitively identify what study drug a participant is receiving to provide optimal care. We will only break the blind if knowledge of the study drug in Phase 1 (escitalopram or placebo) is necessary to provide optimal treatment in an emergency situation. If the emergency situation is an adverse event, this will be recorded and reported as such. Emergency unblinding will be conducted through the Vanderbilt Investigational Drug Service, who is providing study drug and blinding procedures. They have 24-hour access for emergency unblinding.
3. **Antidepressant Side Effects:** We will formally assess side effects at each planned contact and informally as needed through additional or unscheduled calls. We will attempt to minimize side effects by slow titration and allowance for dose reduction if needed. We will withdraw subjects from the study if they cannot tolerate the lowest dose of 10mg of escitalopram or placebo equivalent during phase 1 or 150mg of bupropion xl during phase 2.

We describe below some of the more common or particularly concerning side effects. There is always the potential for the development of rare, unanticipated side effects. In general, we will carefully assess subjects with new complaints to determine if they may be related to study drug and if there is a need for closer monitoring or change in study drug dosing.

- a. **Escitalopram common side effects:** Although generally well tolerated, escitalopram does carry risk of side effects. These include: dermatological (rash), gastrointestinal (dry mouth, nausea, diarrhea, constipation), neurological (dizziness, vivid dreams), systemic (fatigue, somnolence or insomnia, appetite change, weight loss/gain, sweating), and sexual dysfunction.
 - b. **Bupropion common side effects:** Likewise, bupropion is generally well tolerated. Common side effects include: dermatological (rash), gastrointestinal (nausea, diarrhea, constipation, dry mouth), neurological (dizziness, headache, tinnitus, tremor, vivid dreams), psychiatric (anxiety, agitation), or systemic (insomnia, appetite and/or weight loss, sweating). There are also rare risks of seizures or Stevens-Johnson syndrome, which we address through our entry criteria.
 - c. **Suicide risk:** Antidepressant-induced suicidality is an important concern and one that has resulted in a black-box warning on antidepressants by the FDA. We will both inform subjects of this potential risk and monitor for suicidality at each contact. Should any possible suicidality be detected, a study doctor will assess that individual and act accordingly (see Item 1 above).
 - d. **Discontinuation Syndrome:** Discontinuation syndrome, seen with abrupt cessation of antidepressant drugs, may cause a variety of neurological (dizziness, vertigo, insomnia, tremor, paresthesias), gastrointestinal (nausea, abdominal cramping), systemic (lethargy, flu-like symptoms) and psychiatric symptoms (irritability, anxiety, dysphoria). We will provide a medication taper for individuals who wish to stop escitalopram at the study's end.
4. **Risk of Placebo:** The primary concern with use of placebo is that individuals receiving placebo will fail to improve or worsen over the course of the placebo period. We minimize this risk by using a shorter study (8

weeks in contrast to 10 or 12 weeks) and use of withdrawal criteria, including worsening depression (“stopping rules” – see Section 12 below). We further minimize this risk by an unequal allocation of subjects in phase 1 to escitalopram or placebo in a 2:1 ratio. Such an approach is feasible as we are not testing for drug efficacy but examining neural predictors of remission, which we hypothesize would differ between escitalopram and placebo.

5. Antidepressant Medications: End of Study Procedures: During the course of the study we will work with study subjects to identify providers who will continue their care at the end of the study. For those subjects who wish to continue on their end-of-study drug, we will provide prescriptions, two free visits, and assist with arranging follow-up clinic visits with their provider. If they do not wish to continue on study drug, we will also refer to clinical providers, but also work to slowly discontinue the study drug to avoid discontinuation effects.
6. Magnetic Resonance Imaging. Although this procedure is generally low-risk, there are particular concerns. Individuals will be screened for the presence of implanted metal (including but not limited to medical devices, shrapnel, tattoos or permanent makeup); those who screen positive will be excluded from the study. Claustrophobia is also an issue for many potential subjects. During the MRI, subjects will have voice contact with a radiology technician, and may request the scan be stopped at any time.
7. Incidental Findings: Magnetic Resonance Imaging: Another risk is the occurrence of incidental findings on MRI. All scans are reviewed at time of acquisition and concerning findings are discussed with an attending neuroradiologist. Should any concerning findings be seen, a study doctor will convey these findings to the subject along with recommendations for further evaluation, and facilitate referrals for such evaluation and treatment.
8. Breach of confidentiality: There is the potential risk of breach of confidentiality of clinical, genetic, and laboratory information. The PI, [name], has extensive experience as a clinical investigator dealing with such sensitive information, and as a previous member of an Institutional Review Board has experience assuring that data is adequately protected. Safeguards to protect confidentiality include locked records and firewalls around password-protected electronic data, and all study data being coded, with the key linking the code with a subject’s identity being kept in a separate, locked file.

13.0. ADVERSE EVENT REPORTING:

We define an adverse event as any adverse change in health or development of a side effect occurring in a study participant after enrollment. These may be expected events (known drug effects, as detailed in the consent form, safety monitoring plan, or package insert) or unexpected events. We define a serious adverse event as any event that results in hospitalization, disability or permanent damage, is life threatening, results in death, or any other serious event that does not fit these outcomes, but require urgent medical intervention.

We will carefully monitor adverse events throughout the study. Subjects will be assessed for safety, medication tolerability, and unanticipated problems at each contact. Emergency contact information will be

provided to each subject for urgent, unanticipated problems. All adverse events will be reviewed by [name] at least weekly. All AEs, regardless of being judged as related or non-related, will be summarized and included in the annual IRB continuing review. All SAEs will be reported to the Vanderbilt IRB and VA TVHS IRB within 7 working days. [name] will have responsibility for this reporting requirement. Additionally, working in collaboration with the IRB, he will assure that reportable adverse events are also reported to NIH.

As this study will use FDA approved antidepressant medications, is not a multi-site clinical trial, and is not a Phase III clinical trial, we will not establish a formal DSMB for this study. As Phase 1 is placebo-controlled and blinded, we did consider initiation of a DSMB but in conjunction with NIH program officers ultimately decided it was not necessary due to the long history of experience with escitalopram, its overall tolerability, and excellent safety profile. Per NIH request, prior to initiating enrollment we have named [name] as the independent safety monitor. He will review all safety events in a blinded format every 6 months while subjects

are participating in the study. If, after reviewing the blinded data, he is concerned about adverse event rates, he may request unblinded data. In addition to other reporting requirements, he will also review any serious adverse events (SAEs) within 7 days. [name] conclusions after each data review will be provided to the Vanderbilt IRB and VA TVHS IRB with each continuing review.

